4.1. Introduction

Data processing, tabulation of descriptive statistics, calculation of inferential statistics, and graphical representations will be performed primarily using SAS (release 9.4 or higher). If the use of other software is warranted, the final statistical methodology report will detail what software was used for what purposes.

Continuous (quantitative) variable summaries will include the number of subjects (n) with nonmissing values, mean, standard deviation (SD), standard error (SE), median, minimum, and maximum.

Categorical (qualitative) variable summaries will include the frequency and percentage of subjects who are in the particular category or each possible value. In general, the denominator for the percentage calculation will be based upon the total number of subjects in the study population for the treatment groups, unless otherwise specified. The denominator for by-visit displays will be the number of subjects in the relevant study population with nonmissing data at each study visit.

The minimum and maximum will be reported with the same degree of precision (i.e., the same number of decimal places) as the observed data. Measures of location (mean and median) will be reported to 1 degree of precision more than the observed data and measures of spread (SD, SE) will be reported to 2 degrees of precision more than the observed data.

Percentages will be presented to 1 decimal place, unless otherwise specified and with the following exceptions: a percentage of 0% will not be displayed (i.e., only the count of 0 will be displayed), and a percentage of 100% will be displayed with 0 decimal places.

Unless otherwise indicated, all statistical tests will be conducted at the 0.05 significance level using 2-tailed tests, and *P* values will be reported. Corresponding 95% confidence intervals (CIs) will be presented for statistical tests. A *P* value of ≤ 0.10 but > 0.05 will be considered evidence of a trend.

4.2. Interim Analysis and Data Monitoring

The DSMB will meet after 15 subjects in Cohort A have completed at least 28 days of double-blind treatment to review aggregate safety and tolerability data (including PK concentration data, PK parameters, and ECG results). The safety data will be unblinded. At that time, the DSMB will decide whether Cohort B (adults and subjects aged 12–17) may begin enrolling, or if additional adult safety data are required before allowing subjects aged 12 – 17 to participate in the study. The DSMB will meet again after 60 subjects have enrolled in the study. The sponsor may request additional reviews, e.g., should any other findings/issues pertaining to safety emerge requiring DSMB review. Details of the DSMB operation will be developed in conjunction with the members of the DSMB before the first meeting and will be modified as required. The unblinded DSMB outputs will not be seen by anyone except the DSMB and the performing statistician.

The primary analysis period is the first 90 days of treatment (i.e., the Double-blind Period). Overall unblinding will take place at the end of the Double-blind Period of the study only after database lock has been achieved. The data will be cleaned and frozen and an unblinded analysis of the data will be performed. The data will be considered final at this point and no changes to these data will be permitted following unblinding with the exception of outcomes and end dates of ongoing AEs and concomitant mediations. A second analysis will take place for endpoints assessed from Day 90 through the OLE.

The protocol assumes a 20% dropout/non-evaluable rate. This rate will be continuously monitored throughout the COVID-19 pandemic. In the event that this rate dramatically increases, a blinded sample size reestimation may be performed to ensure statistical power for the primary endpoint is maintained using the assumptions in Section 3.2.

5. Analysis Populations

The following 5 analysis populations are planned for the Double-blind Period of this study:

- **Safety:** all subjects who are randomized to treatment and receive at least 1 application of study drug in the Double-blind Period. This population will be the primary population for analyses of safety. Subjects will be analyzed by actual treatment received.
- **Intent-to-treat (ITT):** all randomized subjects. This population will be used as the primary population for the analysis of efficacy for the Double-blind Period of the study. Subjects will be analyzed by randomized treatment.
- **Modified intent-to-treat (mITT):** all subjects in the Safety population with at least 1 postbaseline assessment of efficacy in the Double-blind Period. Subjects will be analyzed by randomized treatment.
- **Per-protocol (PP):** subjects in the mITT population who met all inclusion criteria and no exclusion criteria, were compliant with study drug application, and who had no significant protocol deviations. Subjects will be analyzed by actual treatment received.
- **Pharmacokinetic (PK):** all subjects in the Safety population who have at least 1 plasma sample with quantifiable concentration. This population will be used to summarize all PK endpoints. Subjects will be analyzed by actual treatment received.

The following analysis populations are planned for the OLE of this study:

- **OLE Safety:** all subjects who complete the 90-day Double-blind Treatment Period and receive at least 1 application of study drug in the OLE.
- **OLE ITT:** all subjects who complete the 90-day Double-blind Treatment Period and sign the OLE informed consent.
- **OLE mITT:** all subjects in the OLE Safety population with at least 1 assessment of efficacy after Visit 6.
- **OLE PP:** all subjects in the OLE mITT population who met all inclusion criteria and no exclusion criteria, were compliant with study drug application from baseline through EOT, and who had no significant protocol deviations throughout the study.

Since all subjects in the OLE are to receive trifarotene cream HE1 200 µg/g, analyses will be by actual treatment received.

Inclusion in the analysis populations will be determined prior to database lock. Deviations related to COVID-19 will also be evaluated in determining PP population eligibility.

6. General Issues for Statistical Analysis

6.1. Statistical Definitions and Algorithms

6.1.1. Baseline

The last nonmissing assessment recorded prior to the first dose of treatment in the Double-blind Period will be used as the baseline observation for all calculations of change from baseline, including those in the OLE.

6.1.2. Adjustments for Covariates

If there is a statistical difference among treatment groups with respect to baseline characteristics, that variable may be added to the statistical models as a blocking factor or covariate to determine the effect on treatment. Age group and baseline score are planned for inclusion in statistical models, unless otherwise indicated. Age group will be categorized as adolescents (ages 12 to 17 years, inclusive) and adults (≥ 18 years).

6.1.3. Multiple Comparisons

No adjustments will be made for multiple comparisons. All *P* values for the secondary and exploratory endpoints will be provided in the summary tables for informational purposes only.

6.1.4. Handling of Dropouts or Missing Data

All possible efforts will be made to ensure that subjects stay in the study and all data are collected as scheduled. Withdrawn subjects will not be replaced. If a substantial number of subjects are withdrawn from the study, the sponsor will evaluate the need for developing replacement criteria. Randomized subjects withdrawn from the study may not reenter.

Missing endpoint values in this study may result from subjects discontinuing from the study prematurely or missing intermediate assessments while remaining on study. To assess the effect of missing data on the primary efficacy analysis, a sensitivity analysis will be performed using multiple imputation (MI) for the Double-blind Period only. Multiple imputations will be used to replace missing IGA outcomes using multiple draws from the posterior predictive distribution estimated from the vehicle treatment. The IGA scores will be imputed and then categorized as treatment success.

Sensitivity analyses to investigate robustness to missing data will be performed for the primary endpoint as described in [Section 8.1.2](#).

Missing safety data and data for secondary endpoints will not be imputed.

6.1.5. Analysis Visit Windows

Visits will be analyzed as scheduled. Unscheduled and/or repeated measurements will only be included if a scheduled measurement is not available and the unscheduled/repeated measurement falls within the analysis visit windows as described in Table 3. The windows follow the Schedule of Events in Table 1 and Table 2. Unscheduled/repeated measurements will be listed.

Table 3: Analysis Visit Windows

Visit	Target Start Day	Lower Limit	Upper Limit
1		-97	-1
2	1	1	1
3	14	9	19
4	30	23	37
5	60	53	67
6	90	83	97
7	104	99	109
8	120	113	127
9	150	143	157
10	180	173	187
11	194	194	194

Visit windows may be extended (as reasonable) so as to accommodate delays for assessments due to the COVID-19 pandemic.

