3.4. Treatments Administered

For the Double-blind Treatment Period, a fixed dose (determined at Visit 2) of trifarotene cream HE1 100 µg/g or 200 µg/g or vehicle cream will be applied topically twice weekly on up to 90% body surface area (BSA) of each subject. Trifarotene cream HE1 is a cream containing 100 or 200 µg/g (0.01% [w/w] or 0.02% [w/w], respectively) of CD5789. Vehicle contains the same ingredients, without the CD5789. Trifarotene cream HE1 and vehicle will be provided in cream form for topical application and will be packaged in 50-g tubes from which up to 36 g of investigational product (IP) may be dispensed per application, i.e., the maximum dose per

application. Study staff will apply the first dose of study drug to each subject in the clinic on Day 1 after baseline measurements, and will record the amount of study drug applied.

Thereafter, each subject will apply approximately the same amount (up to 36 g) of study drug as for the first dose on up to 90% of BSA twice weekly, sparing the scalp, inguinal, and axillary areas. Subjects will receive an adequate number of tubes to use 1 tube per application and will use a new tube for each treatment day.

For the OLE, all subjects will receive trifarotene cream HE1 200 µg/g and apply the same fixed dose in the same manner as in the Double-blind Period for an additional 90 days.

If the treatment causes application site reactions, the frequency of application will be reduced or interrupted only on the area of concern, as indicated herein. During all clinic visits, the investigator will assess local tolerability (Scale: 0-3 [none, mild, moderate, severe]) for stinging/burning, pruritus, erythema) for each body area (chest/abdomen, back, arms, legs, and face/neck), and the following procedures will be followed:

- If a score of 2 (moderate) is recorded on a local tolerability assessment scale (stinging/burning, pruritus, erythema) on any treated area, the study drug will be applied on that area only once weekly, until the score is back to <2. Continue to treat all other areas twice weekly provided the score is <2 on those areas.
- If a score of 3 (severe) is recorded on a local tolerability assessment scale (stinging/burning, pruritus, erythema) on any treated area, the study drug will not be applied on that area until the score is back to <3 (i.e., “drug holiday”). Continue to treat all other areas twice weekly provided the score is <2 on those areas.

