7.4. Exposure and Compliance

Compliance by tube weight and compliance by number of doses will be summarized by treatment group using descriptive statistics. The total weight of tubes dispensed and returned, as well as total number of tubes dispensed, returned, and returned unused will also be summarized. This analysis will be conducted for the Safety population and for the OLE Safety population.

A subject is compliant with study product if he or she takes at least 80%-120% of the scheduled doses as assessed by number of doses taken reported, supplemented by tube weight and diary entries. The number and percentage of subjects who were compliant will be tabulated by treatment group for the Double-blind Period and overall for the OLE. Derivations of compliance are defined in Section 6.1.7.

All initial study drug application, drug accountability (dispensed and returned), and subject diary data collected will be listed. Changes in treatment administration or treatment dispensation due to COVID-19 including start and end dates of change, method of alternative administration/dispensation, dosing interruptions, and relevant changes to compliance expectations (weights or tube counts) will be documented from the COVID-19 visit impact log.

8. Efficacy Analysis

All efficacy endpoints will be summarized using the ITT population. The primary analysis will be repeated in the mITT and PP populations.

Summaries of efficacy variables in the OLE will be provided using the OLE ITT. Primary IGA summaries will also be provided for the OLE mITT and OLE PP populations. For continuous efficacy analyses using MMRM, only formal comparisons of change from baseline will be performed in the OLE. No other formal inferential analyses will be conducted for efficacy variables in the OLE.

All efficacy data, regardless of population, will be presented in data listings.

If alternative methods are used for capturing efficacy assessments (i.e., in person not on site at the subject's home, remotely with visual aid, or remotely via telephone), additional sensitivity or subgroup analyses may be performed to assess the potential impact to efficacy analyses. These will be delineated as ad hoc analyses in the CSR.

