9.5. Local Tolerability

During all clinic visits, the investigator will assess local tolerability (Scale: 0-3 [none, mild, moderate, severe]) for each treated body area (chest/abdomen, back, arms, legs, and face/neck).

Descriptive summaries of the investigator's assessment of erythema, stinging/burning, and pruritus will be presented by body area, period, treatment group, and study visit.

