Severe	XX (XX.X%)	XX (XX.X%)	XX (XX.X%)	XX (XX.X%)	XX (XX.X%)
Stinging/Burning					
None	XX (XX.X%)	XX (XX.X%)	XX (XX.X%)	XX (XX.X%)	XX (XX.X%)
Mild	XX (XX.X%)	XX (XX.X%)	XX (XX.X%)	XX (XX.X%)	XX (XX.X%)
Moderate	XX (XX.X%)	XX (XX.X%)	XX (XX.X%)	XX (XX.X%)	XX (XX.X%)
Severe	XX (XX.X%)	XX (XX.X%)	XX (XX.X%)	XX (XX.X%)	XX (XX.X%)
Pruritus					
None	XX (XX.X%)	XX (XX.X%)	XX (XX.X%)	XX (XX.X%)	XX (XX.X%)
Mild	XX (XX.X%)	XX (XX.X%)	XX (XX.X%)	XX (XX.X%)	XX (XX.X%)
Moderate	XX (XX.X%)	XX (XX.X%)	XX (XX.X%)	XX (XX.X%)	XX (XX.X%)
Severe	XX (XX.X%)	XX (XX.X%)	XX (XX.X%)	XX (XX.X%)	XX (XX.X%)

Note: Percentages are n/Number of subjects in the Safety population within actual treatment group and overall*100.
[1] Baseline is defined as the last non-missing assessment recorded prior to the first dose of treatment in the Double-blind Period.
SOURCE: Listing 16.2.9.3

Programming note: Continue for Back, Arms, and Legs. Visits will be Baseline [1], Day 14, Day 30, Day 60, and Day 90.

Table 14.3.6.3.2
Summary of Local Tolerability Assessments by Study Visit
OLE Safety Population

Same shell as Table 14.3.6.3.1

Programming note: Continue for Back, Arms, and Legs. Visits will be Baseline [1], Day 104, Day 120, and Day 150. Update Note: to read "Note: Percentages are n/Number of subjects in the OLE Safety population within treatment group*100. All subjects received Trifarotene cream HE1 200 ug/g in the OLE." Add OLE = open label extension to Abbreviations.

Table 14.3.6.4.1
Summary of Physical Examination Results by Study Visit
Safety Population

Study Visit: XXXXX

Body System Result Clinically Significant?	Trifarotene cream HE1 100 ug/g (N=XX)	Trifarotene cream HE1 200 ug/g (N=XX)	Overall Trifarotene cream HE1 (N=XX)	Vehicle (N=XX)	Overall (N=XX)
Body System 1					
Not Done	XX (XX.X%)	XX (XX.X%)	XX (XX.X%)	XX (XX.X%)	XX (XX.X%)
Normal	XX (XX.X%)	XX (XX.X%)	XX (XX.X%)	XX (XX.X%)	XX (XX.X%)
Abnormal	XX (XX.X%)	XX (XX.X%)	XX (XX.X%)	XX (XX.X%)	XX (XX.X%)
Yes	XX (XX.X%)	XX (XX.X%)	XX (XX.X%)	XX (XX.X%)	XX (XX.X%)
No	XX (XX.X%)	XX (XX.X%)	XX (XX.X%)	XX (XX.X%)	XX (XX.X%)
Body System 2					
Not Done	XX (XX.X%)	XX (XX.X%)	XX (XX.X%)	XX (XX.X%)	XX (XX.X%)
Normal	XX (XX.X%)	XX (XX.X%)	XX (XX.X%)	XX (XX.X%)	XX (XX.X%)
Abnormal	XX (XX.X%)	XX (XX.X%)	XX (XX.X%)	XX (XX.X%)	XX (XX.X%)
Yes	XX (XX.X%)	XX (XX.X%)	XX (XX.X%)	XX (XX.X%)	XX (XX.X%)
No	XX (XX.X%)	XX (XX.X%)	XX (XX.X%)	XX (XX.X%)	XX (XX.X%)
...					

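### The by-visit local tolerability tables can understate how many subjects in each arm ever had a moderate or severe local reaction, and no table counts subjects whose application was reduced or interrupted

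*SAP*

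**What the plan says.** Comparing the safety of two concentrations with vehicle is part of the primary objective (Section 2.1.1), and local tolerability by body area is a named safety endpoint (Section 2.2.1).

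- **Assessment.** Section 3.4: "During all clinic visits, the investigator will assess local tolerability", on a 0-3 scale.
- **Effect of a score on dosing.** At a score of 2, "the study drug will be applied on that area only once weekly, until the score is back to <2". At a score of 3, "the study drug will not be applied on that area until the score is back to <3". Other areas continue to be treated.
- **Tolerability summaries.** Section 9.5: the summaries "will be presented by body area, period, treatment group, and study visit". The programming note to Table 14.3.6.3.1 reads "Visits will be Baseline [1], Day 14, Day 30, Day 60, and Day 90".
- **Unscheduled scores.** Section 6.1.5: "Unscheduled and/or repeated measurements will only be included if a scheduled measurement is not available", and the value must also fall in a Table 3 window. Otherwise, "Unscheduled/repeated measurements will be listed".
- **Areas not treated.** Subjects record these in the diary, for instance when a local reaction is the cause (Table 1 footnotes). Listing 16.2.5.3 has columns for areas not treated, reasons and cream reaction. Section 7.4 says only that "subject diary data collected will be listed".

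**The concern.** The tolerability question in a trial of two concentrations and vehicle is how many subjects in each arm had a reaction bad enough to change how the product was used. The planned tables answer a different question: how many subjects had a given score on a given visit day. The two can diverge for three reasons:

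- The same or different subjects may make up the counts at successive visits.
- A score recorded at an unscheduled visit is usually kept out of the tables.
- After a score of 2 or 3 the affected area receives less product or none, so a later low score in that subject does not show that twice-weekly application was tolerated.

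Two arms could therefore show similar by-visit profiles although one had more subjects with reduced or interrupted application. Nothing planned for the tables would reveal that.

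**Working it through.** The SAP states no tolerability rate, so there is no figure to reproduce. The check is one of logic and of reading the planned outputs together.

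**1. What a by-visit count can say about ever reacting.** For one arm, let S(v) be the set of subjects scored 2 or 3 at scheduled post-baseline visit v, and U the set scored 2 or 3 at an unscheduled assessment that Section 6.1.5 keeps out. The number who ever reacted is E = |S(14) ∪ S(30) ∪ S(60) ∪ S(90) ∪ U|.

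- Lower bound: E ≥ the largest single |S(v)|.
- For scheduled scores alone, the union lies between the largest |S(v)| and the sum of the |S(v)|.
- The tables give no information on U, so they set no upper limit on E.

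Hypothetical counts show the ambiguity. If 3 subjects are severe at Day 14 and 3 at Day 30, that is at least 3 and at most 3 + 3 = 6 distinct subjects, before any unscheduled score. Section 1 reports 65 subjects enrolled. On the assumption of an equal split, 65/3 ≈ 22 per arm, so each subject is worth about 1/22 ≈ 4.5 percentage points.

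**2. What Section 6.1.5 does to an unscheduled score.**

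| Scheduled score | Unscheduled score | Unscheduled score tabulated? |
|---|---|---|
| Present | In window | No, listed only |
| Present | Outside window | No, listed only |
| Missing | In window | Yes |
| Missing | Outside window | No, listed only |

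Unscheduled visits are foreseen (Table 1 footnote on remote visits), so the rule can act on real data.

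**3. Whether another table counts reduced or interrupted application.**

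- *Dose count.* Section 3.4 provides one tube per application. Section 6.1.7 counts doses as tubes returned minus tubes returned unused. A subject who skips one area and treats the rest still uses a tube, so this measure does not change.
- *Tube weight.* Section 6.1.7 divides weight used by weight dispensed. Skipped areas would lower it, but so would any other under-use, so the cause cannot be identified.
- *Diary.* It holds the needed facts dose by dose, but only Listing 16.2.5.3 uses them.
- *Adverse events.* Section 9.1 counts each subject once over the period by preferred term, severity and relationship. Nothing in the SAP makes each score of 2 or more an adverse event.

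**4. Gaps in the same shells.** The shells cover chest/abdomen, back, arms and legs, but not face/neck, which Section 9.5 names. The open-label shell stops at Day 150, although Table 2 schedules tolerability at Day 180. The shell's denominator is the Safety population, while Section 4.1 uses subjects with nonmissing data at the visit. These are separate from the main point, but new rows built on the shells would inherit them.

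**The case against.** The other side has a good case, and much of it stands.

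- The dosing rule acts on scores recorded at clinic visits. A score of 2 or 3 at Day 14, 30, 60 or 90 is tabulated at that visit. Only a reaction confined to the time between scheduled visits is missing from the tolerability tables altogether.
- Section 6.1.5 is not an absolute exclusion: an in-window unscheduled score replaces a missing scheduled one, and everything is listed.
- Telephone contacts at Days 7 and 45 review adverse events and diaries. Treatment-emergent event tables span the whole period, and events leading to withdrawal of study drug are tabulated separately. It would go too far to say that tolerability by concentration cannot be read from the planned output at all.
- By-visit tables describe prevalence on a visit day. The SAP does not present them as cumulative incidence, so Sections 6.1.5 and 9.5 do not conflict. Safety is descriptive only.

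Three stronger readings are tempting and are not supported:

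- A reader might infer that the dosing rule clears reactions before the next visit and so hides them. The SAP gives no episode durations.
- A reader might put a percentage on the missed episodes by assuming onset times and durations. Any such figure would come from those assumptions and from the visit schedule, not from Section 6.1.5. It would also include episodes never scored by anyone, which a worst-score row could not recover.
- A reader might extend the point to laboratory and ECG values, because Section 6.1.5 is general. The dosing rule has no link to those values, and Section 9.2 already provides a separate listing of abnormal laboratory results with all visits for the parameter.

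None of this supplies a per-subject count of moderate or severe reactions, or of reduced or interrupted areas.

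**Conclusion.** The point holds as an improvement to the planned output, not as a contradiction in the SAP. With the shell's fixed Safety denominator, the by-visit tables can equal or understate the share of subjects in each arm who ever scored 2 or 3. Recorded unscheduled scores are normally excluded, and later scores in subjects who reacted also reflect reduced exposure. No planned table counts those subjects.

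The direction follows from the definitions and needs no assumption about how long reactions last. The size cannot be calculated: it depends on how many scores of 2 or 3 are recorded at unscheduled visits, and on how far the same subjects recur across visits. The SAP gives neither. Adverse event tables reduce the gap by an unknown amount. Because comparing safety by concentration is a primary objective and the data are already collected, the change should be made.

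**What to change.** 1. **Section 6.1.5.** State that the exclusion of unscheduled and repeated values applies to by-visit summaries only.
2. **Tables 14.3.6.3.1 and 14.3.6.3.2.** Add the worst post-baseline score per subject, by body area and overall, for each of erythema, stinging/burning and pruritus, by treatment group, from all scheduled and unscheduled assessments. In the open-label table, use scores after the Day 90 visit, so that double-blind scores are not counted again.
3. **One diary-based table.** From the data behind Listing 16.2.5.3, give the number and percentage of subjects per arm with at least one area reduced or not treated because of a local reaction.
4. **While editing the shells.** Reconcile the body areas with Section 9.5, the open-label visits with Table 2, and the denominator with Section 4.1.

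The dosing rule in Section 3.4 is not touched. The cost is a few rows, one short table, and possibly less favourable tolerability figures. Section 1 says the plan is filed before any unblinded analysis; if the additions are made by then, they remain prespecified.

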3.5. Method of Assigning Subjects to Treatment Groups

Subjects will be randomized in a 1:1:1 ratio to trifarotene cream HE1 100 µg/g or 200 µg/g or vehicle cream in the Double-blind Period.

Subjects who continue into the OLE will receive trifarotene cream HE1 200 µg/g and apply the same fixed dose in the same manner as in the Double-blind Period for an additional 90 days.

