3.7. Schedule of Events

A detailed schedule of events for the Double-blind period of the study is provided in [Table 1](#). A detailed schedule of events for the OLE is provided in [Table 2](#).

Table 1: Schedule of Events for Double-blind Period

	Screening (-97 days to -1 day) Washout up to 90 Days ^a	Double-blind Treatment Period						
		Baseline (Day 1)	Telephone Visit (Day 7)	Day 14 ± 5 days	Day 30 ± 7 days	Telephone Visit (Day 45)	Day 60 ± 7 days	Day 90 ^{b,c} ± 7 days (ET)
Visit	1	2		3 ^d	4 ^d		5 ^d	6 ^d
Written informed consent/assent	X							X ^a
Assign screening number	X							
Inclusion/exclusion criteria	X	X						
Demographics	X							
Medical history	X							
Physical examination	X	X ^e						X ^e
Vital signs (blood pressure and pulse)	X	X		X	X		X	X
Height, weight, and BMI	X							X ^b
IGA assessment ^f	X	X		X	X		X	X
VIIS ^g assessment	X	X		X	X		X	X
Roughness assessment ^h	X	X		X	X		X	X
Palm/sole assessment	X	X		X	X		X	X
Palm/sole fissuring assessment ⁱ	X	X		X	X		X	X
Ectropion score	X	X		X	X		X	X
Photographs ^j		X			X			X
Quality of life per Dermatology Life Quality Index (DLQI)		X		X	X		X	X
EQ-5D Quality of Life Questionnaire		X		X	X		X	X
12-lead ECG ^k	X	X			X			X

	Screening (-97 days to -1 day) Washout up to 90 Days ^a	Double-blind Treatment Period						
		Baseline (Day 1)	Telephone Visit (Day 7)	Day 14 ± 5 days	Day 30 ± 7 days	Telephone Visit (Day 45)	Day 60 ± 7 days	Day 90 ^{b,c} ± 7 days (ET)
Visit	1	2		3 ^d	4 ^d		5 ^d	6 ^d
Clinical laboratory tests (hematology, chemistry, urinalysis) ^l	X	X			X			X
Serology (hepatitis B surface antigen, hepatitis C)	X							
Coagulation panel		X			X			X
Pregnancy test for female subjects (serum at Screening; urine subsequently) ^m	X	X			X		X	X
Randomization via IWRS		X						
PK blood sample collection ⁿ		X		X	X		X	X
Initial study drug application by clinic staff and measurement ^o		X						
Application instructions, advice on emollient and sunscreen use		X	X	X	X	X	X	X
Dispense study drug and diaries ^p		X		X ^p	X ^p		X ^p	(X) ^p
Concomitant medications	X	X	X	X	X	X	X	X
Tolerability assessment		X		X	X		X	X
Adverse events (and review diaries)		X	X	X	X	X	X	X
Collect all used/unused study drug ^q				X	X		X	X
Provide information about OLE option					X	X	X	X

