Abbreviations: BMI = body mass index; DLQI = Dermatology Life Quality Index; ECG = electrocardiogram; ET = early termination; HEENT = head, eyes, ears, nose, throat; ICF = informed consent form; IGA = Investigator’s Global Assessment; IWRS = interactive web response system; OLE = open-label extension; PK = pharmacokinetic; WOCBP = women of childbearing potential; VIIS = Visual Index for Ichthyosis Severity

- a. Upon signing informed consent and entering the Screening Period, subjects will stop using physical and medical treatments for LI, including balneotherapy, and begin to washout prohibited topical and systemic treatments with designated washout periods, as applicable. Before asking a subject to enter washout, investigators should confirm the subject meets study eligibility criteria, except for LI severity (Inclusion Criterion #3). Washout may be up to 90 days. After completing any necessary Washout Period, subjects must return to the site within 35 days before the Baseline Visit within the 97-day Screening Period to have their LI severity assessed and study eligibility requirements determined. During washout, subjects may continue their standard of care of visible skin (face and scalp) for cosmetic reasons and of extremities (palms/soles) to avoid functional consequences on walking or moving their fingers. In the US/EU, this may include compounded emollients with keratolytics (alpha or beta hydroxyl acids) and/or urea. The investigator should approve and document these standard of care treatments in the electronic case report form (eCRF). If the standard of care treatments of the face and/or palms/soles contain prohibited medications, they must be stopped at the Baseline Visit. Subjects may shower, but not bathe or swim, during the Screening Period.
- b. Day 90 procedures should be conducted for subjects who terminate the study early. If a subject discontinues IP, but continues to attend clinic visits, Day 90 will occur as scheduled. Day 90 will be the first visit of the OLE for subjects who choose to continue. Subjects who decide to continue into the OLE will have the following additional procedures: 1) sign informed consent; 2) will be weighed; 3) will be instructed on study drug application; 4) will be given new diaries, and 5) will be provided with study drug.
- c. A Follow-up telephone call will be made within 14 days after Day 90 to subjects who choose not to continue into the OLE to assess any ongoing adverse events.

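### The Visit 6 analysis window has no cut-off at the first open-label application, so in uncommon cases a value taken on open-label 200 µg/g could stand in as double-blind Day 90 data

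*SAP*

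**What the plan says.** **The substitution rule (SAP 6.1.5).** Visits are analysed as scheduled. "Unscheduled and/or repeated measurements will only be included if a scheduled measurement is not available", and then only if "the unscheduled/repeated measurement falls within the analysis visit windows as described in Table 3". Table 3 gives Visit 6 a target of Day 90 with limits of Day 83 and Day 97. The limits are inherited from the visit schedule: "The windows follow the Schedule of Events in Table 1 and Table 2". A further sentence loosens them: "Visit windows may be extended (as reasonable) so as to accommodate delays for assessments due to the COVID-19 pandemic".

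**The start of open-label treatment (SAP 3.7 and 3.5).** Note b to Table 1 states: "Day 90 will be the first visit of the OLE for subjects who choose to continue". At that visit, continuing subjects "will be provided with study drug". Section 3.5 sets the treatment: "Subjects who continue into the OLE will receive trifarotene cream HE1 200 µg/g". This covers all three randomized arms.

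**The period the endpoint belongs to.** Sections 2.2.2.1 and 8.1.1 place the primary endpoint in the Double-blind Period. Sections 3.6 and 4.2 describe that period as the first 90 days of treatment.

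**The concern.** The Visit 6 window is fixed in study days and is the same for every subject. The switch to open-label drug happens at a visit that can fall anywhere inside that window. For an OLE entrant, the part of the window after Visit 6 is therefore open-label time, yet 6.1.5 tests only the study day and whether a scheduled value exists.

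The 90-day comparison with vehicle is the primary objective for both safety and efficacy (2.1.1). A post-switch value entered in the vehicle Day 90 row would be a value on active drug. One entered in the 100 µg/g row could reflect 200 µg/g. An IGA scored after the switch would also come from an investigator who knows that the subject is on active drug.

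**Working it through.** **Inputs**
- Day 90 visit: ±7 days (Table 1).
- Visit 6 analysis window: Days 83 to 97 (Table 3).
- OLE entry and drug supply: at the Day 90 visit (Table 1, note b).
- OLE dosing frequency: twice weekly (3.1).

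**Reproducing the window.** 90 − 7 = 83 and 90 + 7 = 97, as in Table 3. Target day ± visit tolerance also reproduces Table 3 for Visits 3 to 10, so the windows do follow the schedule. The inclusive length for Visit 6 is 97 − 83 + 1 = 15 days.

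**Window remaining after Visit 6.** Days left = 97 − day of Visit 6. Expected applications ≈ 2 × days left / 7.

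| Visit 6 on | Days left in window | Expected open-label applications |
|---|---|---|
| Day 83 | 14 | 4.0 |
| Day 86 | 11 | 3.1 |
| Day 90 | 7 | 2.0 |
| Day 93 | 4 | 1.1 |
| Day 97 | 0 | 0 |

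These are upper limits. Note b says that drug is supplied at the visit; it does not say that the first open-label dose is applied that day.

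**Does another rule close the gap?**
- 6.1.1 ends the baseline period at the first double-blind dose. There is no counterpart at the end of the Double-blind Period.
- 6.1.4 and 8.1.2 impute missing IGA values in a sensitivity analysis, but a value supplied by windowing is no longer missing and would not be imputed. Missing safety data are not imputed, so 6.1.5 is the only stated route that fills those cells.
- Table 2 schedules no OLE laboratory test or ECG before Day 120 (window from Day 113). A repeat taken on Days 84 to 97 after an early or on-time Visit 6 therefore has only the Visit 6 window to fall into.

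**With a cut-off.** If the upper limit is the earlier of Day 97 and the first open-label application, the overlap is 0 days for every OLE entrant. Other subjects keep Days 83 to 97.

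**The case against.** The strongest reply is that the route is narrow. A note to Table 2 says that Day 90 efficacy, safety, laboratory and PK assessments carry over into the OLE without being repeated. Between Visit 6 and Visit 7, Table 2 schedules only a telephone contact. An error needs a subject who attends Visit 6, lacks the scheduled value, still enters the OLE, and has an unscheduled measurement by Day 97. This stands. It makes an IGA error unlikely, although remote Visit 6 assessments (Table 1, note d) keep it possible.

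The second reply is that the intent is plain: the endpoint is double-blind, OLE safety has its own population (section 9), and OLE endpoints belong to a second analysis (3.6, 4.2). A reader might infer that the SAP plans to count open-label data as double-blind. It does not. But those statements are not data-selection rules, and 6.1.5 as written does not apply them.

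Three further inferences go too far:
- **That the COVID-19 clause opens the window without limit.** Delaying the whole visit also delays OLE entry and adds no overlap. Only an assessment delayed separately from OLE entry matters.
- **That the error always narrows the difference.** This is the tendency for a vehicle subject. A 100 µg/g subject measured on 200 µg/g could shift the comparison either way.
- **That the Visit 7 to 11 windows must be re-anchored to OLE start.** Scheduled visits are analysed as scheduled, so re-anchoring would affect only rare substitutions, and the OLE has no comparison between treatments.

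**Conclusion.** The gap is real and small. Followed literally, 6.1.5 allows a measurement taken after up to 14 days of open-label exposure (7 days if Visit 6 is on Day 90) to be analysed as a double-blind Day 90 value. The 14-day figure assumes the earliest permitted Visit 6, application starting at once, and a repeat on Day 97.

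The case is uncommon: an OLE entrant with an unavailable scheduled value and a later repeat by Day 97, most plausibly a laboratory test or ECG. Those data are summarized without formal inference (section 9), so the usual consequence would be a wrong entry in a descriptive row. The SAP gives no count of such cases, and none can be derived from it. A reader might infer that the primary comparison is materially contaminated, or might attach a percentage of the vehicle arm to the problem; any such figure would rest on an assumed count. The point merits correction because the rule is wrong for these subjects and the repair costs almost nothing.

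**What to change.** Add to 6.1.5, with a footnote to the Visit 6 row of Table 3: for subjects who enter the OLE, a value may be used for Visit 6 / Day 90 only if it was taken before the first open-label application, including where a window is extended for COVID-19; measurements taken later are assigned to the OLE only. Subjects who do not enter the OLE keep Days 83 to 97. The Visit 7 to 11 windows need no change for this purpose.

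The rule can be programmed, because the diaries capture the day and time of each application. The cost is one sentence, one footnote, and a few Day 90 cells that stay missing rather than being filled with open-label values. It should be in place before the unblinded analysis.
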